In addition to CQI Team meetings, overall project team meetings occur monthly (at a minimum), with project leaders across MER and AVANCE in attendance, to ensure the partnership remains strong and that coordination across organizations is on track. This recurring, ongoing meeting structure is conducive to close coordination, ensuring that challenges can be quickly addressed, and promising strategies can be efficiently maximized.

One of the key components of this coordination effort is the CQI Data Manager, who is a MER employee, embedded with AVANCE. The CQI Data Manager functions to bridge the gap between organizations. They will interact with AVANCE staff daily while completing their job duties and play a leadership role in the recurring meetings outlined above. See Section II.D above for more details about this role and others. Both the meetings and the roles outlined above will continue throughout the entire project period, providing opportunities to ensure the rigor and relevance of the evaluation and its findings, and to discuss and coordinate dissemination efforts (which will also be shared across MER and AVANCE).

MER has experience operating prior RCT evaluations using this exact process. Clearly outlining roles and responsibilities maintains the independence of the evaluation. That is, the evaluation team helps identify and illuminate areas of concern or improvement (for the program and the evaluation), but the program staff have responsibility for implementing improvements and providing direct services to participants. In this way, AVANCE and MER acknowledge our shared interest in and responsibility for a well-executed project and evaluation, but that MER is also an independent and external organization with a high level of integrity and is not responsible for nor invested in the specific outcomes of the program. This allows for close coordination without allowing for co-dependence or personal interests to influence evaluation findings.

III. Data Collection

A. Data collection

Table 6: Constructs and measures/data collection instruments

Construct	Measure	Instrument	Reliability and Validity (if standardized instrument, you provide a citation for the instrument)
Partner Relationship Attitudes	9 items: levels of agreement with relationship beliefs (categories, 4-point); 3 items: likelihood of key relationship beliefs (categories, 5-point scale)	nFORM Healthy Marriage Youth Program Survey (A1.a-i; A2.a-c)	nFORM
Sexual Attitudes	7 items: levels of agreement with key sexual attitudes (categories, 4-point scale)	nFORM Healthy Marriage Youth Program Survey (B1.a-g)	nFORM
Partner Relationship Behavior	5 items: levels of reported skill with key relationship behaviors (categories, 4-point scale); 6 items: frequency engage in key relationship behaviors (categories, 5-point scale)	nFORM Healthy Marriage Youth Program Survey (C1b.a-e; C3.a-f)	nFORM
Financial Attitudes	4 items: levels of agreement with key financial	OLLE (Online Local	In appendix D of: Jurkiewicz, T. & Friedman, L. (2020). Impact Evaluation of The TYRO

	attitudes (categories, 7-point scale)	Evaluation) Survey	Champion Dads Project in Dallas, Texas: Final Impact Evaluation Report for Anthem Strong Families. Midwest Evaluation and Research.
Employment Attitudes	4 items: levels of agreement with key employment attitudes (categories, 7-point scale)	OLLE (Online Local Evaluation) Survey	In appendix D of: Jurkiewicz, T. & Friedman, L. (2020). Impact Evaluation of The TYRO Champion Dads Project in Dallas, Texas: Final Impact Evaluation Report for Anthem Strong Families. Midwest Evaluation and Research.

Consent:

Because the planned evaluation involves human subjects, AVANCE understands program implementation requires both IRB approval and participant informed consent. MER has an established relationship with Solutions IRB, having secured more than 14 IRB approvals and renewals for evaluations it has conducted during the past four years. IRB clearance will be submitted for approval and obtained during the planning period.

Each school location will have a signed letter of agreement to be included in this project. This must be filed with the IRB during the application process. Any school locations that are later recruited into the study will result in MER submitting amendments to the IRB to include these schools as research sites, and the additional school's letter will be included in the project.

An opt-out letter will be provided to all parents/guardians of applicants under the age of 18 who are interested in the project. The letter will state that because this is a research study, survey data will be collected on youth, but will be kept confidential. If a parent or guardian does not want their child to participate in the project, that letter will need to be signed and returned to the school or facilitator.

During the survey administration process, youth participants will be given a letter along with the survey that explains that the survey is optional, any or all questions can be skipped for any reason, and not taking the survey will not result in any penalties.

Table 7: Data Collection Timeline

Wave of Data Collection (e.g., baseline, short-term follow-up, long-term follow-up)	Timing of Data Collection
Baseline	Collected immediately following informed consent and enrollment – during orientation or first workshop

Post-test	Collected after the completion of the primary services programming – during the last workshop or session
1 year follow-up (post-enrollment)	Collected approximately one year after program enrollment

Table 8: Measures

Measure	Timing of Data Collection (baseline, wave of data collection)	Method of Data Collection	Who Is Responsible for Data Collection?
On-line Local Evaluation (OLLE) and nFORM Baseline Survey	Baseline	Participant self-enters survey using online data collection program or completes survey with program staff through Zoom or over the phone in the case of virtual service delivery	Data Manager and program staff will proctor data collection and assist participants as necessary
OLLE and nFORM Post-Test Survey	Post-Test (approx. 7 weeks after enrollment for standard format and 16 days after enrollment for compressed format)	Participant self-enters survey using online data collection program or completes survey with program staff through Zoom or over the phone in the case of virtual service delivery	Data Manager and program staff will proctor data collection and assist participants as necessary
OLLE 1 Year Follow-up Survey	1 year after enrollment / baseline	Participant self-enters survey using online data collection platform and link – or – Phone interview data collection	MER Research Staff/ participant tracking team

Ensuring and monitoring high quality data collection:

This evaluation will utilize both post-program surveys (completed at the completion of core programming) and follow-up surveys collected one year after enrollment. The methods for these data collections differ. The primary driver for post-program survey completion is high rates of program retention. This data point will be collected during the last workshop session – after (but during the same session of) the completion of the nFORM post-program data collection. As such,

only those individuals who complete the program and who are at the data collection session will participate in the post-program data collection.

All program staff and evaluation staff will undergo a rigorous set of trainings to prepare for the evaluation. All staff receive an overview and introductory training to present the goals and objectives of the evaluation effort and its importance to the overall project. Next, all staff receive training on human subjects protection and are required to pass a certification test on the subject matter. All staff will also receive a detailed training on the evaluation, including the evaluation tools, timing and data collection process, and the role and importance of randomization of participants.

In addition, the CQI Data Manager and the primary local evaluation staff will undergo a rigorous training process to better understand the context of HMRF research, training on data collection procedures they will be responsible for, and training on the nFORM system and use of nFORM data in a CQI process. MER is creating networks of CQI data managers and Evaluation Project Managers across the 12 projects that we are evaluating so that all staff have access to experienced data managers and evaluation staff who have done this work previously. This training takes the form of weekly training sessions that are currently underway.

Members of the CQI team will also receive specific training on the MER CQI process that has been developed prior to the launch of data collection or program services. As described elsewhere, MER is assisting the program staff in implementing a robust CQI process that will focus on retention as one of the primary areas of program improvement, and as such, we are anticipating relatively modest levels of attrition for this data collection.

On a bi-weekly basis, the CQI Data Manager, the local evaluation staff, and MER technical specialists will be responsible for downloading data from the nFORM and MER On-Line Local Evaluation (OLLE) systems for processing and presentation to the CQI team for tracking and monitoring performance measurement outcomes (recruitment, enrollment, dosage, completion, referrals, etc.) so that near real-time adjustments can be made to program implementation to ensure compliance with program goals and objectives.

All MER training is currently being recorded, and as new staff come on board with projects or project staff turnover (or need refresher training), recorded training material can be shared and accessed with follow-up one on one training with the primary local evaluator and the MER LOB Lead, who has more than 15 years' experience in evaluating HMRF projects.

Tracking participants and reducing attrition:

For each wave of data collection listed in Table 7, what is your estimated response rate?	Baseline	100% - done at the time of enrollment
	Wave 1	90% - estimated A-HFP completion rate
	Wave 2	70% - estimated 1 year follow-up rate

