In this study, a descriptive study design will be used to determine if A-HBF participants benefit from the *Survival Skills for Healthy Families (SSHF)* curriculum. At-risk or homeless youth who agree to participate in the study will receive the *SSHF* curriculum through either a series of 7 in-school weekly workshops (14 hours) or an intensive weekend retreat co-attended by their parents (16 hours) followed two weeks later by a Reflections Workshop (2 hours). All program participants also receive support services delivered by Family Coaches and Career Coaches as needed.

Baseline data will be collected from participants shortly following study enrollment. Post-test data will be collected following curriculum completion, approximately 2-7 weeks following study enrollment depending on the curriculum delivery format. Follow-up data will be collected one year after study enrollment.

B. Methods to develop study groups

Because this is a descriptive evaluation, this subsection is not relevant.

C. Sample

The target population for this study is at-risk and homeless youth from high-need school districts in Harris County who are 14-18 years of age and enrolled in 9-12th grades. AVANCE will work with school districts, school boards, and individual schools to identify and recruit participants from the target population. The unit of analysis for this study is individual youth. See Appendix D for anticipated sample flow and attrition rates.

Power analysis:

The analysis of survey data will address the primary and secondary research questions with findings derived from running a linear regression model that quantifies the potential benefits of Building Futures Program participation and outcomes as well as the relationship of participant characteristics to Building Futures Program benefits. Benefits are quantified by specifying a model that compares the relative influences of participant characteristics as predictor that is regressed against a series of dependent variables (e.g., outcomes specified in the logic model). Given the predicted sample size as described in the appended logic model, the following calculations regarding power and effect size can be made.

	Participant Responses	Minimum Detectable Effect Size
Post-test	1105	0.017
Follow-up	774	0.023

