These power analyses assume an Alpha Level of 0.05 with a two-tailed test and power level set at 0.80 (1 – Beta). The estimated effect sizes are all small effects or nearly small effects that would be detected, based on best practices outlined by Cohen (1988) of small effect sizes <0.02 and medium effect sizes <0.15. With these analyses, the proposed research design is demonstrated to measure large, medium, and small changes in participants' responses.

Table 4: Methods to Promote Sufficient Program Participation

What methods will you use to ensure sufficient sample is recruited, enrolls, and participates in the program?	AVANCE will work with schools and their community partners to recruit program participants, and AVANCE will provide incentives for program retention and completion. The CQI process will address issues regarding program recruitment and enrollment to ensure targets are met.
Who will be responsible for recruiting the evaluation sample?	The evaluation sample will not differ from the program population, in that all participants will be invited to participate in the evaluation. Enrollment into the evaluation will be conducted by the CQI Data Manager who will conduct the informed consent process and proctor the baseline data collection efforts.

Please describe any incentives to be offered for program participation and/or completion and/or data collection and/or participation in the evaluation.

Program Participation – AVANCE will provide a series of incentives for program retention (promotional items) and completion (\$75 gift card).

Evaluation Participation – No incentives will be used for the first two data collections- baseline and post-test, while participants are beginning or still engaged in services. A \$50 incentive will be used for the 1-year follow-up survey and will be provided in the form of a Walmart gift card.

D. Lead staff

See Appendix B for CVs of lead evaluation staff.

Table 5: Lead Evaluation Staff

Name	Organization	Role in the Evaluation
[name]	Midwest Evaluation and Research	Principal Investigator
[name]	Midwest Evaluation and Research	Lead Evaluation Consultant
[name], MA	Midwest Evaluation and Research	Evaluation Project Manager
[name]	Midwest Evaluation and Research	CQI Data Manager

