To measure the impact of dosage in hours on change in pre to post-survey, a regression analysis will be conducted. Specifically, a multiple regression analysis will be conducted with dosage in hours as the predictor variable and change in the dependent variables (partner relationship attitudes, sexual attitudes, partner relationship behavior, financial attitudes, and employment attitudes) as the outcome variables. The model will control for the format of the SSHF curriculum and support services, as well as any demographic variables that are significantly related to the outcome variables.

Assumptions of linear regression, such as normality of residuals, homoscedasticity, and linearity, will be checked using diagnostic plots and statistical tests, such as the Shapiro-Wilk test for normality and the Breusch-Pagan test for homoscedasticity. If the assumptions are violated, appropriate transformations or non-parametric tests will be used. Additionally, the potential for multicollinearity among the predictor variables will be assessed using variance inflation factor (VIF) values. A VIF value greater than 10 indicates problematic multicollinearity, and steps will

be taken to address this issue, such as excluding highly correlated predictor variables. Overall, this study will use regression analysis to examine the relationship between dosage in hours and change in the dependent variables, while controlling for relevant covariates

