### Model Specification to Predict Outcomes With Dosage

Construct by Outcome	Dependent Variables (follow-up)	Response Codes for Dependent Variables	Dependent Variable Type	Independent Variables
Primary outcome:				
Partner Relationship Behavior: 6 scaled items	DISAG_BE_FU	1 = none of the time to 5 = all of the time	Continuous	Dosage of curriculum; co-variates (using pre-survey scores)
5 scaled items	REL_BE_FU	1 = I am extremely good at this to 4 = I am extremely bad at this		
Secondary outcomes:				
Partner Relationship Attitudes: 9 scaled items	PARTREL_ATT_FU	1 = strongly agree to 4 = strongly disagree	Continuous	Dosage of curriculum; co-variates (using pre-survey scores)
3 scaled items	PARTREL_FUT_ATT_FU	1 = almost no chance to 5 = almost certain		
Sexual Attitudes: 7 scaled items	SEX_ATT_FU	1 = strongly agree to 4 = strongly disagree		
Financial Attitudes: 4 scaled items	FIN_ATT_FU	1 = strongly disagree to 7 = strongly agree		
Employment Attitudes 4 scaled items	EMP_ATT_FU	1 = strongly disagree to 7 = strongly agree		

Step 4 – run the linear regression model: Procedures to run the linear regression model are influenced by dependent variable types. Standard regression is necessary to model the influence of curriculum dosage on continuous dependent variables, such as when participants respond to

---

multiple items in a scaled construct by indicating levels of agreement with statements about key partner relationship attitudes.

Step 5 – interpret model results: Model results demonstrate the benefits of A-HBF participation whenever dosage variables predict more positive primary and secondary outcomes for a construct. For primary outcomes, benefits of receiving *SSHf* curriculum confirm hypotheses when respondents with higher levels of participation more frequently report ( $p < .05$ ):

1. Healthy partner relationship behavior

For secondary outcomes, benefits of receiving *SSHf* curriculum confirm hypotheses when respondents with higher levels of participation more frequently report ( $p < .05$ ):

2. More positive attitudes about partner relationships
3. More positive attitudes about sexual relationships
4. More positive attitudes about financial readiness
5. More positive attitudes about job readiness

---

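### The dosage regression has no school or delivery-mode term and treats youth as independent, so the hours slope may have too small a standard error and may be confounded by setting

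*Protocol*

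**What the plan says.** **Settings.** Protocol II.C recruits through many units: "AVANCE will work with school districts, school boards, and individual schools to identify and recruit participants from the target population". The consent text in III.A says "Each school location will have a signed letter of agreement to be included in this project", and allows schools to join later as research sites. The individual youth is the unit of analysis.

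**Delivery.** Protocol II.A describes "a series of 7 in-school weekly workshops (14 hours) or an intensive weekend retreat co-attended by their parents (16 hours", the retreat being followed by a Reflections Workshop. Virtual delivery is not mentioned there. It appears only in the survey-method column of Table 8, in the baseline and post-test rows, where a participant "completes survey with program staff through Zoom or over the phone in the case of virtual service delivery".

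**Dosage model.** SAP IV.A says "The model will control for the format of the SSHF curriculum and support services", and adds demographics found to be significantly related to the outcome. The table headed Model Specification to Predict Outcomes With Dosage lists the independent variables as "Dosage of curriculum; co-variates (using pre-survey scores". Neither place names school or delivery mode. The supplied text has no random effect and no cluster-robust error.

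**Reading of the result.** Step 5 takes a dosage slope with p < .05 in the favourable direction as confirming the hypotheses for the primary and secondary outcomes.

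**The concern.** There is no comparison group, so the Step 5 rule depends on why hours differ between youth. Timetable, absence and facilitator can plausibly make hours differ by school, and virtual sessions may be attended differently. Two consequences follow.

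- **Precision.** If hours are alike within a school and so are outcome changes, youth in that school do not supply independent information on the slope. The ordinary standard error is then too small, even with no confounding.
- **Confounding.** If schools or modes with more attended hours also differ in one-year change for other reasons, part of that difference enters the hours slope.

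The existing controls do not cover this. The format term separates weekly workshops from the retreat, but not one school from another within the weekly format, nor virtual from in-person. School and mode are not demographics, so the significance rule for covariates would not bring them in. Change scores or pre-survey scores remove stable school differences in level, but not differences in change.

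**Working it through.** **Inputs from the documents.** N is 1105 at post-test and 774 at follow-up (0.70 × 1105 = 773.5). The stated test settings are: "These power analyses assume an Alpha Level of 0.05 with a two-tailed test and power level set at 0.80".

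**Inputs assumed.** 20 schools of 38 youth (760 in all), hours and outcome change in SD units, true hours slope zero. ICC means the share of variance between schools.

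**1. The plan's own figure.** The power table has the row "Post-test 1105 0.017" and gives 0.023 for N = 774. Neither the number of predictors nor the effect-size scale is stated. On the f² scale, a joint test of 14 predictors gives 0.0168 and 0.0241. On the R² scale it gives 0.0165 and 0.0235, close to both. Nothing indicates an allowance for clustering. The point does not depend on these figures.

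**2. Clustering alone.** The variance of the slope is understated by about 1 + (m − 1) × ICC(hours) × ICC(change), with m = 38. The actual size of the test is 2 × [1 − Φ(1.96/√factor)].

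| ICC hours | ICC change | Factor | 1.96/√factor | Size by formula | Simulated |
|---|---|---|---|---|---|
| 0.2 | 0.03 | 1 + 37 × 0.006 = 1.222 | 1.773 | 7.6% | 8% |
| 0.2 | 0.05 | 1 + 37 × 0.010 = 1.370 | 1.675 | 9.4% | 10% |
| 0.3 | 0.05 | 1 + 37 × 0.015 = 1.555 | 1.572 | 11.6% | 12% |

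School terms return the size to 4–5%. These rates are two-sided. Step 5 counts only the favourable half, so they mean about 4–6% against a nominal 2.5%.

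**3. School effects correlated with hours.** The expected spurious slope is about r × √(ICC hours × ICC change). For comparison, the ordinary standard error is about 1/√760 = 0.036.

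| ICC hours | ICC change | r | Spurious slope | As planned | Cluster-robust | School terms |
|---|---|---|---|---|---|---|
| 0.1 | 0.02 | 0.3 | 0.013 | 7.5% | 6.1% | 5.0% |
| 0.2 | 0.03 | 0.5 | 0.039 | 19.3% | 14.2% | 5.0% |
| 0.3 | 0.05 | 0.5 | 0.061 | 40.0% | 25.8% | 4.3% |

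The last three columns are simulated false-positive rates (3000–4000 runs). Repeat simulations agreed within about two percentage points. A negative r biases the slope against the programme by the same amount.

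**4. Virtual delivery, N = 774.** Let p be the virtual share, and let hours be lower by a and change lower by b. The spurious slope is p(1 − p)ab / [1 + p(1 − p)a²].

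- p = 0.3, a = 1, b = 0.2: 0.042/1.21 = 0.035. Simulated false positives are 18%, and 5% with a mode indicator.
- p = 0.2, a = 0.5, b = 0.2: 0.016/1.04 = 0.015. The rates are about 7% and 5%.

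**5. When nothing happens.** With 15 schools and N = 774, school effects on change (ICC 0.05) with no clustering of hours gave a slope of 0.001 and 5.7% false positives. A virtual effect of −0.2 SD unrelated to hours gave 0.000 and 5.8%.

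**The case against.** A reader might infer that setting differences are necessarily credited to curriculum hours. The documents do not support that: confounding needs hours and outcome change to move together across settings, and they report neither. Step 5 of the working shows no bias without that link. The sign could also go against the programme.

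A reader might also infer that the problem is purely bias and not one of standard errors. The figures contradict this. Cluster-robust errors remove (19.3 − 14.2)/(19.3 − 5) = 36% of the excess in the middle case, and 41% and 56% in the strongest and mildest. Clustering is the more certain part, though robust errors alone leave any confounding in place.

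It would be too strong to say that all five hypotheses would be falsely confirmed. Each simulation covers one outcome, and the SAP also assigns the research questions to a repeated-measures ANOVA. Nor is a virtual arm planned. Table 8 describes a contingency, and its one-year row gives everyone the same online or phone options.

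The strongest argument concerns the remedy. More motivated youth may attend more within a school, and school terms do not remove that. They can even discard cleaner variation if hours between schools reflect only timetables. Suppose a spurious within-school slope of 0.05 SD, with 20% of hours variance between schools and N = 774. False positives are then about 20% without school terms (slope 0.04, standard error 0.036) and 24% with them (0.05 and 0.040). This stands as a limit on what the slope can show. It does not justify ignoring schools. For retreat youth, school need not identify the group they were taught in.

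Finally, the supplied procedure starts at Step 4. Steps 1–3 might contain a fuller covariate list, so the omission is established only for the text supplied.

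**Conclusion.** The point holds in conditional form. Several schools, possible virtual delivery, and a dosage model with neither term are all in the documents. If hours cluster by school, the false-positive rate is about 8–12% under the assumed ICCs (hours 0.2–0.3, change 0.03–0.05). If setting is also related to one-year change, it runs from about 7% in a mild case to 20–40% in stronger ones. Confounding that favours the programme would make Step 5 overstate the evidence for benefit; the opposite sign would hide benefit. The number of schools, the ICCs, the correlation and the virtual share are all assumed. The study is declared descriptive, so this is a worthwhile improvement to the dosage analysis and does not invalidate the evaluation.

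**What to change.** In SAP IV.A and the model specification table:

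- Add school as a pre-specified term in every dosage regression, whatever its p-value. For retreat youth use the retreat cohort. Pool very small units by a rule fixed in advance.
- If any delivery is virtual, add an in-person versus virtual indicator on the same terms.
- Report attended hours by school or cohort and by delivery mode.
- In Step 5, describe the dosage slope as an association, because self-selection within a school remains.

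In protocol II.A, name virtual delivery as a possible mode so that design and analysis agree with Table 8.

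**Cost.** This is mainly wording. School should be identifiable from recruitment and site agreements; retreat cohort and delivery mode need to be recorded for each youth. The statistical price is that between-school variation in hours is no longer used. If 20–30% of hours variance lies between schools, the slope's standard error rises by a factor of 1/√(1 − 0.2) = 1.12 to 1/√(1 − 0.3) = 1.20, that is, about 12–20%.
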